Step 8 – Visit #4: Alzheimer's Disease Dementia Risk Disclosure with (D+)/without (D-) Amyloid Scan results (in-person)

All participants will return to the study site for their fourth in-person visit to receive their Alzheimer's Disease Dementia Risk Assessment either with or without their amyloid imaging result, as determined by random assignment. At each site, a trained disclosure provider will present the participant with generalized reference curves of Alzheimer's disease risk based on age, gender, family history, and race/ethnicity. If the participant is randomized to receive their amyloid imaging result, the disclosure provider will communicate whether they have elevated or not elevated amyloid and present his/her AD dementia risk estimate compared to the general population.

If the participant is randomized to not receive their amyloid imaging result at this visit, but will receive their scan result at the end of the study, the disclosure provider will only present the participant's AD dementia risk estimate based on age, gender, family history, and race/ethnicity.

The participant will have the opportunity to ask questions.

Step 9 – Phone Call #4: 1-3 Day Safety Check

The study coordinator will call the participant in 1-3 days to assess the participant's status as a safety check to assess any psychological impact of the disclosure visit, regardless if they are in the immediate scan disclosure group or delayed scan disclosure group.

Psychological impact of the disclosure visit will be measured by using the Impact of NeuroImaging for Alzheimer's Disease (INI-AD) scale adapted to this study to measure the impact of amyloid imaging for AD⁵³ and using the intrusion subscale of the Impact of Event Scale (IES). The INI-AD scale is a 16-item multi-dimensional assessment of risk disclosure across distress, uncertainty, and positive experience.

The INI-AD was developed and validated in our prior REVEAL trials, and will be adapted for this safety check by phone to allow for differentiation of the emotional effects of risk disclosure from more general distress or worry.

The IES-intrusion subscale, a 7-item self-reported measure,⁵⁴ assesses response related to a specific stressful life event, and has been specifically anchored to test-related distress in studies of the impact of health risk information, including all previous REVEAL Study trials.

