Analyses of IES as the main secondary outcome and of other measures, will be conducted in a similar fashion. While our main focus for the IES will be upon the contrast between the A+D+ and A-D+ groups, we will also contrast the A+D+ and the D- groups (as long as the A+D- and A-D- exhibit similar outcomes). The D- group may experience increased distress waiting for the disclosure of their imaging, which could reduce our power to explore comparisons between A+D+ and D- groups, although we did not see this occurring in our prior REVEAL studies when participants in the non-disclosure arms were waiting for their genotype data at the end of the study. It will also be of interest to compare the difference between A+D- and A-D- groups, because this comparison would reveal any differences in cognition due to the amyloid burden

itself among participants who do not learn their amyloid status at the fourth visit. We do not expect to find any difference here in only 6 months of follow-up. For Exploratory Aims 1.2 and 2.3, we will examine regression models or MMRM models with interaction terms for race and group to evaluate whether the differences at 6 months between the groups (e.g. A+D+ vs A+D-) are similar for AAs and non-AAs. Point estimates will be considered in addition to confidence intervals and p-values.

For the 6-month follow-up visit digit-span task, we will examine whether working memory performance and pupil dilation responses differ when under high than low threat differentially depending on both disclosure status and amyloid levels.

For the 6-month visit digit-span task, we will examine whether working memory performance and pupil dilation responses differ when under high than low threat differentially depending on both disclosure status and amyloid levels.

Power Calculation

Our objective is to achieve 80% power to detect a difference of moderate effect size (0.4-0.6 SD units) on the primary outcome of ADCS-PACC mean score between the A+D- and A+D+ groups at 6 months.

Assuming a PACC standard deviation of 2.2⁴⁴, 50 individuals per group would provide 80% power to detect a difference of 1.25 PACC units (0.52 SD units) between A+D- and A+D+ at 6 months.

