Primary Analysis 1.1: For this aim we focus on one outcome, ADCS-PACC, and thus use an alpha level of 0.05 to determine statistical significance. First, we will obtain descriptive statistics for those who are in the D+ and D- groups among A+ subjects. Then, we will compare ADCS-PACC scores between D+ and D- groups among A+ subjects using a two-sided test of means. Next, we will compare D+ and D- groups on potential confounders. We will initially consider confounders due to the Covid-19 pandemic (as described below) and then consider other confounders (including age, education, premorbid function, experiences of discrimination). If any are significantly different between the two groups ($p < 0.05$), despite randomization, we will conduct regression analysis adjusting for those confounders that are different. Analyses will be repeated measures (6 wks. and 6 mos.) adjusting for baseline measure at time of randomization. We will focus on 6 month differences, but also check for time-averaged differences between D+ and D- groups. Check ADCS-PACC for normality. If normal, linear regression analysis for repeated measures can be used, specifically a mixed-effects model with repeated measures (MMRM). If not normal, we will use an appropriate transformation to make the distribution more normal. We will also conduct an Intention-to-Treat (ITT) analysis, which will incorporate information from those who drop out over the 6 months, assuming missing at random. This analysis will have better control of type 1 error and power. We will model time as a categorical measure, and the primary outcome will be the estimated difference (contrast) between the two groups (D+ and D-) at 6 months and secondarily the time-averaged difference. We will also apply a model with 3 repeated measures (baseline, 6 wks., 6 months) without adjustment for baseline ADCS-PACC to examine the full trend over time, but this will be a secondary analysis.

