Exploratory Analysis 1.3: The analysis will be the same as the primary analysis, but now conducted only in the African Americans in the study. If the hypothesis is true, we expect a larger difference, but the study is not powered for this subgroup analysis. To formally test whether African Americans have a greater response, we will perform analyses of the full group of A+ individuals, adding an interaction term to the model for race * disclosure group.

Aim 2: To determine whether disclosure of elevated brain amyloid will cause psychological distress.

Study Subjects: All Study Participants and the subgroup of A+ subjects

Outcomes: IES (Impact of Event Score), measured twice (6 wks., 6 mos.), and INI-AD, measured twice (6 wks., 6 mos.)

Hypothesis 2.1: At 6 weeks after disclosure, A+D+ participants will have greater IES scores and INI-AD scores than A-D+ or D- participants.

Analysis 2.1: Analysis will generally use the same methods as Aim 1. For this Aim, IES is the primary outcome for which we will use an alpha level of 0.05. INI-AD is a secondary outcome. Our main focus for this aim is contrasting scores between the A+D+ and A-D+ groups. We will also contrast the A+D+ and the D- groups (as long as the A+D- and A-D- exhibit similar outcomes). As in Aim 1, we will obtain

descriptive statistics between the two groups (A+D- and A-D+ for the first contrast and then A+D- vs the D- group). We will also evaluate the confounding effect of Covid-19 as described in Aim 1 and subsequently other potential confounders for these contrasts and incorporate if needed in further regression analyses. Note that there is no IES at baseline. So there is no adjustment for a baseline measure. The same holds true for INI-AD. One major difference here is that the IES and INI-AD are not normally distributed and cannot be transformed to become so. Thus, we will use generalized linear models fit with generalized estimating equations using a log link and a gamma distribution. If needed, we will add a value of 1 to all scores to shift the distribution away from zero and use a log transform on the data. We will focus on the differences at 6 weeks, but also evaluate the time-averaged differences.

Exploratory Hypothesis 2.2: Comparison of outcomes at 6 weeks and 6 months after disclosure will show African Americans to be equally vulnerable to psychological distress as measured by IES and INI-AD after amyloid imaging compared to all other racial and ethnic groups.

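### Aim 2 fits IES and INI-AD by GEE with no stated handling of missed visits, so distress-related dropout could bias the distress contrasts

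*SAP*

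**What the plan says.** SAP Aim 2 lists IES and INI-AD at 6 weeks and 6 months. IES is the primary outcome of the aim at alpha 0.05. On estimation, Analysis 2.1 says: "Thus, we will use generalized linear models fit with generalized estimating equations using a log link and a gamma distribution". On the comparison it says: "Our main focus for this aim is contrasting scores between the A+D+ and A-D+ groups". On timing: "We will focus on the differences at 6 weeks, but also evaluate the time-averaged differences". It also records: "Note that there is no IES at baseline", and the same for INI-AD.

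On missing data, Aim 2 is silent apart from a general link back: "Analysis will generally use the same methods as Aim 1". In Primary Analysis 1.1 the intention-to-treat analysis of the ADCS-PACC is one "which will incorporate information from those who drop out over the 6 months, assuming missing at random". The protocol's Data Analysis section makes the same assumption for its MMRM and adds: "Analyses of IES as the main secondary outcome and of other measures, will be conducted in a similar fashion". The SAP's multiple imputation, under Missing PACC data, covers components of the PACC and nothing else.

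Protocol Step 9 (Phone Call #4) collects the IES intrusion subscale and the INI-AD from every participant 1-3 days after the disclosure visit. Analysis 2.1 does not mention these scores.

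**The concern.** A likelihood-based MMRM remains valid when dropout depends on scores already observed and in the model. Unweighted GEE generally needs more: dropout must be unrelated to the outcomes, given the covariates. When the SAP replaced the MMRM by GEE for the distress outcomes, it put nothing in place of the lost protection.

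There are two separate routes to bias:

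- **Loss after 6 weeks that depends on the 6-week score.** GEE and a likelihood model differ here. The 6-month and time-averaged results are exposed. The protocol places Hypothesis 2.1 at 6 months, so these results are not trivial.
- **Loss before 6 weeks that depends on early distress.** The main 6-week contrast is exposed. Such a person has no IES in the Aim 2 data, so any model that uses only the 6-week and 6-month IES has the same weakness. The information that could help is the 1-3 day score.

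The outcome measures harm. If people upset by an elevated result return less often, the remaining A+D+ group looks calmer than the group that was randomised.

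**Working it through.** **Inputs.** The documents give no expected mean, spread or power for IES, so the plan has no figure to reproduce. The one relevant input is the protocol's dropout of about 10% (Power Calculation), which relates to completed 6-month visits. Everything else below is assumed.

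**A. Loss before 6 weeks (main contrast).** Assume true 6-week means of 10 (A+D+) and 6 (A-D+), a ratio of 10/6 = 1.67. Scores are gamma with shape 0.5 to 1, linked to the 1-3 day score by a Gaussian copula with correlation 0.5 to 0.7. In A+D+, dropout is p_T in the top quarter of the early score and p_R in the rest; in A-D+ it is random.

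Let w = 0.25(1 − p_T) / [0.25(1 − p_T) + 0.75(1 − p_R)] be the top quarter's share among those who return. The mean of those who return is 10 − (0.25 − w)(m_T − m_R), where m_T and m_R are the true 6-week means in the top quarter and the rest. Drawing 4,000,000 values from the assumed model, m_T − m_R runs from 16.36 − 7.88 = 8.48 (shape 1, correlation 0.5) to 22.49 − 5.83 = 16.66 (shape 0.5, correlation 0.7).

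- *All 10% lost before 6 weeks* (p_T = 25%, p_R = 5%): w = 0.1875/0.90 = 0.2083, so 0.25 − w = 0.0417. Means are 10 − 0.0417 × 8.48 = 9.65 and 10 − 0.0417 × 16.66 = 9.31. Dividing by 6 gives ratios of 1.61 and 1.55. The excess of 0.67 shrinks by 9% to 17%.
- *Half lost before 6 weeks* (12.5%, 2.5%): w = 0.21875/0.95 = 0.2303, so 0.25 − w = 0.0197. Means are 9.83 and 9.67, ratios 1.64 and 1.61. The excess shrinks by 4% to 8%.
- *Same 25%/5% rule in both groups, each by its own top quarter:* both means are multiplied by the same factor (0.965 or 0.931), so the ratio stays at 1.67.
- *Rule in A-D+ only:* 10/(6 × 0.965) = 1.73 to 10/(6 × 0.931) = 1.79, an exaggeration.

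**B. Loss after 6 weeks driven by the 6-week score.** This is a separate large-sample simulation. It assumes a true ratio of 2.0, gamma shape 1, latent correlation 0.6, 10% dropout, and a log-odds slope of 1.0 per 10 points in both groups. The model has a separate mean for each group and visit.

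| Result | Independence | Exchangeable | Weighted GEE |
|---|---|---|---|
| 6 weeks | 2.00 | 2.00 | 2.00 |
| 6 months | 1.87 | 1.95 | 2.00 |
| Time-averaged | 1.93 | 1.97 | 2.00 |

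The time-averaged ratio is the geometric mean of the two visits: √(2.00 × 1.87) = 1.93. The 6-week estimate is unaffected because it equals the observed 6-week group means. With slope 0.5 the 6-month ratios are 1.96 and 2.00. With a true ratio of 1.0 there is no bias. When only comparator dropout was distress-related, the 6-month ratio (independence) rose to 2.08.

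The attenuation in B with one slope for both groups does not contradict the cancellation in A. In B the rule acts on score points, so the group with higher scores loses more people (12.9% against 6.9%). In A the cancelling rule acts on each group's own quartile.

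**The case against.** The strongest reply is that the main result escapes the GEE problem. The contrast of interest is at 6 weeks, the first full IES, and later dropout leaves it unbiased. Where early loss does bias it, a mixed model on the same two visits would be biased too, so changing the estimator alone would cure nothing. This stands. It separates the two routes, but it does not supply a plan for either.

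A reader might also infer that the plan contradicts itself on missing at random. The documents do not go that far. The assumption is written for the ADCS-PACC and reaches Aim 2 only through general cross-references, and the SAP presents the distress model as a major difference. Aim 2 has an unstated assumption, which is a gap and not a contradiction.

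No section gives dropout by group or by distress. Distressed participants are to receive extra contact and referral (protocol, Ensuring Safety of Human Subjects), which may reduce such loss. The same section lists follow-up depression and anxiety scores marked for exclusion. If that were applied after disclosure, loss would depend on observed distress. The documents do not settle which effect would prevail.

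Finally, at about 10% dropout the bias is modest, and an exchangeable working correlation removes part of the later-dropout component. But the SAP names no working correlation, so that protection is not planned.

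**Conclusion.** The concern holds as a correctable gap in Aim 2. Unweighted GEE does not in general have the validity under missing at random that the plan claims for its MMRM, and nothing is specified to restore it. The GEE-specific bias falls on the 6-month and time-averaged results. The 6-week contrast is at risk only from earlier loss related to distress.

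Under the assumptions in the working, the early-loss bias is at most 17% of the excess if all 10% of A+D+ is lost before 6 weeks, and about half that if half is. The method point is secure; the size and sign are not.

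Two stronger readings are tempting. One is that dropout would necessarily make the result look less harmful. The documents support only that it could: the bias is near zero when the dropout pattern is proportionally the same in both groups, and it reverses when stronger in A-D+. The other is that the main contrast measures harm from disclosure. Both of its groups learn their result, so it concerns an elevated versus a not-elevated result. Only the conditional A+D+ versus D- contrast bears on disclosure itself.

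**What to change.** Keep the gamma log-link GEE, and state its working correlation and missing-data assumption in Analysis 2.1. Multiply impute missed IES and INI-AD visits before fitting it. The imputation model should include amyloid-by-disclosure group, the 1-3 day IES-intrusion and INI-AD scores, the Visit 2 GDS and mini-STAI, and the other follow-up visit. Keep that model small, because each A+ group has only about 50 people and the scores are skewed. Inverse-probability-weighted GEE on the same variables is an acceptable alternative.

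Report dropout by group and by 1-3 day score, so that readers can judge direction. Keep the unweighted GEE as a sensitivity analysis. Neither imputation nor weighting on observed scores will in general fully correct loss that depends on the unseen 6-week score itself, and the report should say so.

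The cost is SAP wording, some programming and slightly wider intervals. No new data are needed: these variables are already scheduled, and the SAP already uses multiple imputation for the PACC.

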
At 6 months after disclosure...

Primary Hypothesis 1.1: ADCS-PACC scores will be lower among A+D+ participants than A+D- participants.

Exploratory Hypothesis 1.2: African-Americans will demonstrate a higher level of neuropsychological bias in response to amyloid imaging results than other racial groups due to complex sociocultural reasons which can negatively influence cognitive testing outcomes.

Specific Aim #2: To determine whether disclosure of elevated brain amyloid will cause psychological distress.

At 6 months after disclosure...

Secondary Hypothesis 2.1: A+D+ participants will have greater IES scores than A-D+ or D- participants.

Exploratory Hypothesis 2.2: A+D+ participants will have higher scores on scales of subjective memory complaints than A+D- participants.

Exploratory Hypothesis 2.3: Comparison of outcomes at 6 weeks and 6 months after disclosure will show African-Americans to be equally vulnerable to psychological distress after amyloid imaging as other racial and ethnic groups.

Specific Aim #3: To explore how learning amyloid imaging disclosure will impact preventative health behaviors, advance planning for health (e.g. long-term care insurance decisions) and well-being (e.g. stigma, quality of life and relationships).

Specific Aim #4: To examine whether disclosure of amyloid levels affects performance by inducing stereotype threat.

At 6 months after disclosure...

Quaternary Hypothesis 4.1: The effects of disclosure on task performance will depend upon whether or not the test is described as assessing cognition.

Quaternary Hypothesis 4.2: The effects of disclosure on pupil dilation (a measure of effort and

arousal that is assumed to index stereotype threat) will depend upon whether or not the test is described as assessing cognition.

III. Subject Selection

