Exploratory Analysis 2.2: Analyses will be the same as described above for IES and INI-AD applied to the subgroup of African Americans. To formally test whether effects are the same, we will add an interaction term to the model for race to evaluate whether African Americans experience similar distress as those in the study who are not African American.

Aim 3: To explore how amyloid imaging disclosure will impact preventative health behaviors, advance planning for health (e.g. long-term care insurance decisions) and well-being (e.g. stigma, quality of life and relationships).

Study Subjects: All Study Participants, contrasting D+ and D- participants. Additionally, we will compare the A+D+ subjects to the A-D+ subjects.

Outcomes: We will focus on outcomes at 6 months of follow up after disclosure.

Measures: We have several categories of behavior to examine.

- 1) Preventive Health Behaviors: diet, vitamin intake, physical exercise and mental exercise, medication changes
- 2) Advance Planning: long-term care insurance decisions, other insurance decisions, completion of advance directives
- 3) Well-being: stigma, quality of life and relationships, sharing of information

Aim 3 Hypotheses:

Preventive Health Behaviors:

D+ individuals will show equivalent probability of undertaking preventative health behavior changes as D- individuals.

A+D+ individuals will show a higher probability of undertaking more preventative health behavior changes than A-D+ individuals.

Advance Planning:

Advance planning will occur with a similarly low frequency in D+ and D- individuals.

Advance planning will occur more frequently for A+D+ individuals than A-D+ individuals.

Well-Being:

D+ individuals will report more sharing of information than D- individuals.

Sharing of information will not differ between A+D+ and A-D+ individuals.

D+ individuals will report more stigma compared to D- individuals. This effect will be modified by amyloid status. A+D+ individuals will report more worries about stigma than A-D+ individuals.

D+ individuals will report similar QOL compared to D- individuals. This effect will be modified by amyloid status. A+D+ individuals will report lower levels of quality of life than A-D+ individuals

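### SAP Exploratory Analysis 2.2 uses a race interaction test to support a hypothesis of equal vulnerability, which such a test cannot establish; with about 12 African American A+D+ participants projected, a null result could be misread as support

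*SAP*

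**What the plan says.** Protocol Section II, Exploratory Hypothesis 2.3, predicts that comparison of outcomes at 6 weeks and 6 months "will show African-Americans to be equally vulnerable to psychological distress after amyloid imaging as other racial and ethnic groups". The SAP carries this forward as Exploratory Hypothesis 2.2, under which the outcomes will "show African Americans to be equally vulnerable to psychological distress as measured by IES and INI-AD".

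For the analysis, SAP Exploratory Analysis 2.2 repeats the Aim 2 models in the African American subgroup and then states: "To formally test whether effects are the same, we will add an interaction term to the model for race". The stated purpose is "to evaluate whether African Americans experience similar distress as those in the study who are not African American". The term that race interacts with is not named.

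Other text bears on how the result would be read:

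- For Aim 2, "IES is the primary outcome for which we will use an alpha level of 0.05". The main comparison is given as "Our main focus for this aim is contrasting scores between the A+D+ and A-D+ groups". Aim 2 generally adopts the Aim 1 methods, which include "using a two-sided test of means".
- Protocol Section VI, Data Analysis, covers this same race analysis. It plans race-by-group interaction terms and says that estimates and confidence intervals will be weighed as well as p-values.
- SAP Exploratory Analysis 1.3, on race and the PACC, warns that the study lacks power for that subgroup analysis and names race by disclosure group as the interaction. Analysis 2.2 has neither the warning nor the named partner.
- Neither document gives a similarity margin, an equivalence test, a confidence-interval criterion or a power figure for the race interaction in Aim 2.

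**The concern.** The null hypothesis of an interaction test is that the effects are equal. The test can reject equality but cannot establish it. Here equality is the research hypothesis, so a significant result would contradict the hypothesis, and only a non-significant one is left to support it. The SAP does not say how a non-significant result will be read.

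Low power therefore acts differently in the two race analyses. In 1.3 the hypothesis is a difference, and low power works against it; the SAP gives its warning there. In 2.2 the hypothesis is sameness, and low power makes it easier to appear supported; the warning is absent there.

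At stake is what may be concluded about distress scores in a group that the trial recruits on purpose. The protocol's background section gives understanding the risk-benefit balance in African Americans as a reason for including them.

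**Working it through.** **The plan's own figure.** No power is stated for the race interaction. The projected cells rest on the target of 50 per A+ group (Protocol Section VI, Power Calculation: SD 2.2, difference 1.25 PACC units, 80% power). With two-sided alpha 0.05:

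n = 2 × 2.2² × (1.960 + 0.842)² / 1.25² = 48.6, so 49 per group.

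At 50 per group, power is 81.1% by the normal approximation and 80.3% by the t distribution. The target reproduces.

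**Projected cells.** The inputs are 370 enrolled, about 10% loss and 1:1 allocation (Protocol Sections V and VI), and about 30% A+ and 25% African American (Section II). The 25% share is assumed to hold in every cell.

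- Completers: 370 × 0.9 = 333.
- A+: about 100, so 50 in A+D+.
- A-D+: (333 − 100) / 2 = 116.5.
- African American: 12.5 in A+D+ and 29.1 in A-D+.
- Other: 37.5 in A+D+ and 87.4 in A-D+.

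**Interaction precision.** The documents give no SD for the IES, so the result is in SD units, for one time point on a normal-theory scale:

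SE = √(1/12.5 + 1/29.1 + 1/37.5 + 1/87.4) = √0.1524 = 0.39 SD.

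- 95% CI half-width: 1.96 × 0.390 = 0.77 SD.
- Difference detectable with 80% power: 2.80 × 0.390 = 1.09 SD.

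The protocol calls 0.4 to 0.6 SD a moderate effect. It does so for the PACC, and the range is borrowed here for scale.

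| True race difference | Power | Non-significant |
|---|---|---|
| 0.4 SD | 18% | 82% |
| 0.5 SD | 25% | 75% |
| 0.6 SD | 34% | 66% |
| 0.8 SD | 54% | 46% |

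**Sensitivity.**

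| Change from the base case | SE (SD) | Power at 0.5 SD |
|---|---|---|
| 20% African American (10 in A+D+) | 0.42 | 22% |
| 30% African American (15 in A+D+) | 0.37 | 27% |
| 8 African Americans in A+D+ | 0.44 | 21% |
| 25% A+ | 0.41 | 23% |
| No dropout (closer to the 6-week focus) | 0.37 | 27% |
| A+D+ vs all D- | 0.37 | 27% |
| A+D+ vs A+D- | 0.46 | 19% |

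On the planned log-link scale, with an assumed coefficient of variation of 1.0, the 95% CI for the ratio of ratios extends by a factor of exp(0.765) = 2.15 either way. The factor is 1.84 to 3.15 for coefficients of 0.8 to 1.5.

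**Would an equivalence test help?** With two one-sided 5% tests, the 90% CI half-width is 1.645 × 0.390 = 0.64 SD. That interval cannot fit inside a margin of 0.4, 0.5 or 0.6 SD, so power is essentially zero. With true equality, 80% power needs a margin of (1.645 + 1.282) × 0.390 = 1.14 SD. A 0.5 SD margin would take (1.143 / 0.5)² = 5.2 times the sample, about 1,740 completers.

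**The case against.** The best defence is that the plan already contains much of the right approach. The protocol's Data Analysis section says, for this very race analysis, that estimates and intervals will be considered with p-values, and nothing in the SAP withdraws that. The SAP section on falling short of the planned sample size says a non-significant PACC difference will be read through its confidence interval. The analysis is labelled exploratory in both documents. All of this stands and lowers the weight of the point. None of it says what result would count as similar, and Analysis 2.2 itself describes the interaction term as the formal test of sameness.

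Three stronger readings are tempting, and the documents do not support them:

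- A reader might infer a decision rule under which p > 0.05 proves equality. No section states one; the risk is that a null result could be read that way.
- A reader might infer that the trial is almost certain to confirm the hypothesis whatever the truth. The power figures contradict this: a difference of 0.8 SD would be detected slightly more often than not, and one of about 1.1 SD with 80% power.
- A reader might infer a claim that disclosure is equally safe. Hypothesis 2.2 concerns IES and INI-AD scores. Participant safety rests on individual follow-up, score thresholds, adverse-event reporting and board review, none of which depends on this interaction.

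It is also fair to object that the calculation simplifies the planned gamma, log-link GEE over two visits, and that A+D+ versus A-D+ is an assumed partner because the SAP names none. The sensitivity rows show that the conclusion does not turn on the choice of contrast or on dropout.

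**Conclusion.** The point holds as a mismatch between hypothesis and test. The analysis named in 2.2 cannot support the equality stated in 2.2, there is no margin or interval criterion to fill the gap, and the low-power warning is missing where low power favours the hypothesis. A non-significant result would be the likely outcome even if African Americans differed from others by a moderate amount: 66% to 82% of the time for true differences of 0.6 down to 0.4 SD.

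The count of about 12 is a projection from the plan's targets; the documents do not state it. It assumes that the overall 25% share holds within A+D+. All effect sizes are in SD units because no IES standard deviation is given. The consequence is limited to what may be concluded from an exploratory analysis, but a change of wording before analysis is enough to correct it.

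**What to change.** In SAP Exploratory Analysis 2.2, replace the sentence on formally testing sameness with:

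*The race-by-group interaction (amyloid status within D+ for the main contrast) will be estimated with its 95% CI. The sample size was not chosen to give power for this analysis, and a non-significant interaction will not be taken as evidence of equal vulnerability.*

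Reword Hypothesis 2.2 as estimation, for example:

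*We will estimate how far the effect of disclosure on IES and INI-AD at 6 weeks and 6 months differs between African American participants and all others.*

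A similarity margin is optional. If one is wanted, it must be fixed before analysis, and the team should expect an inconclusive result at any margin of 0.4 to 0.6 SD.

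The change is to SAP wording only and needs no new data or visits. Its downside is that the trial gives up a claim of equal vulnerability and reports a wide interval instead.
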